5.2.5 Prior and Concomitant Therapy

All investigator terms for medications recorded in the eCRF will be coded to an 11-digit code using the World Health Organization Drug Dictionary (WHO DD). The number (percentage) of subjects who took prior and concomitant medications will be summarized on the Safety Analysis Set by treatment group, Anatomical Therapeutic Chemical class, and WHO DD preferred term (PT). Prior medications will be defined as medications that stopped before the first dose of study drug. Concomitant medications will be defined as medications that (1) started before the first dose of study drug and were continuing at the time of the first dose of study drug, or (2) started on or after the date of the first dose of study drug up to the date of the last dose. All medications will be presented in subject data listings. Medications taken within the 12-week Follow-Up Period will also be recorded.

Prior and concomitant therapies for AD and those for non-AD will be summarized separately.

5.2.6 Treatment Compliance

Treatment compliance (%) will be calculated for Safety Analysis set as follows:

$$\frac{\text{Total number of tablets dispensed} - \text{Total number of tablets returned}}{\text{Planned Total number of tablets to be taken}} * 100\%$$

Compliance will be calculated in two ways: compliance up to the last dose (day) of study drug, and overall compliance. Overall compliance will be calculated as the 24-month compliance by assuming each subject has been followed through 24 months in the study; a subject will be considered to take no study drug after study drug discontinuation until the end of 24 months.

Treatment compliance will be summarized using descriptive statistics by treatment group. Subjects will also be categorized by compliance criteria <60%, 60%-80%, 80%-100%, and >100%.

5.3 DATA ANALYSIS GENERAL CONSIDERATIONS

5.3.1 Pooling of Centers

This study has used region as a stratification factor for randomization, therefore, there is no plan to pool any other type of centers or sites.

The regions and corresponding countries that might be included and are grouped together in a particular region are:

1. North America: US, and Canada
2. Western Europe (including Oceania region): Australia, Austria, Belgium, Czech Republic, Denmark, Finland, France, Germany, Hungary, Ireland, Italy, Netherlands, New Zealand, Portugal, Slovakia, Spain, Sweden, Switzerland, and United Kingdom
3. Eastern Europe: Bulgaria, Croatia, Lithuania, Poland, Romania, Russian Federation, and Ukraine
4. Japan
5. China
6. Other Asian countries/regions: Hong Kong, Japan, South Korea, Singapore, and Taiwan
7. South America: Argentina, Brazil, Chile, and Mexico

5.3.2 Adjustments for Covariates of Interest

The primary, secondary, and exploratory efficacy endpoints will include the stratification variables (region, concurrent treatment with AChEIs or memantine, clinical dementia) and baseline value of the endpoint (if applicable) as covariates. In addition, demographic and baseline characteristics covariates of interest will be evaluated in the statistical models, which include:

1. Age treated as continuous and as categorical (<65, ≥65 - <80, and ≥80 years)
2. Sex
3. Race
4. Ethnicity
5. *ApoE4* genotype

5.3.3 Multiple Comparisons/Multiplicity

The primary and secondary endpoints will be tested using a sequential testing procedure at a significance level of 2-sided $\alpha = 0.05$, ie, any test will start only if the test with higher hierarchical order is significant. The hierarchical order for these endpoints is:

1. Change from baseline in the CDR-SB at 24 months (primary endpoint)
2. Time to worsening of CDR scores by 24 months (eg, the worsening of global CDR score is defined as an increase from baseline by at least 0.5 points on the global CDR scale on 2 consecutive scheduled visits at which global CDR is undertaken)
3. Time to conversion to dementia by 24 months for subjects who were not clinically staged as dementia at Baseline based on clinical diagnosis
4. The rate of change over time (mean slope) based on CDR-SB score over 24 months
5. Change from baseline in ADAS-cog₁₄, MMSE, and FAQ at 24 months
6. Change from baseline in ADAS-cog₁₄ Word List (immediate recall and delayed recall) at 24 months
7. Change from baseline in CDR-SB at 27 months (ie, 24 months of treatment plus 3 months posttreatment follow-up)

Analyses on biomarker and exploratory endpoints will be conducted without adjustment for multiplicity.

5.3.4 Examination of Subgroups

Subgroup analysis will be performed for the primary and secondary efficacy endpoints, and also biomarker endpoints. The subgroups include:

- age at baseline (<65, $\geq 65 - < 80$, and ≥ 80 years)
- sex
- race
- ethnicity
- region (section 6.3.1)
- clinical dementia (no, yes)
- concurrent treatment with AChEIs or memantine (no, yes)

- *ApoE4* genotype
- baseline CDR Memory Box score

Forest plot will be generated to visually display the treatment difference with 95% confidence interval, no significance tests will be performed in the subgroups.

5.3.5 Handling of Missing Data

Clinical Assessment

If any item is missing within the CDR, ADAS-cog₁₄, MMSE, and FAQ, then their respective total scores will be missing.

CSF Biomarkers

- If any amyloid β A β 42 measurement is "<LLOQ", then the measurement will be imputed by LLOQ 125 pg/mL.
- If any p-Tau 181 measurement is "<LLOQ", then the measurement will be imputed by LLOQ 16 pg/mL.
- If any Tau measurement is "<LLOQ", then the measurement will be imputed by LLOQ 75 pg/mL.

Others

Adverse events with missing severity will be assigned the highest severity. Adverse events with missing relationship will be assigned the highest relationship.

5.3.6 Other Considerations

Not Applicable.

5.4 EFFICACY ANALYSES

5.4.1 Primary Efficacy Analysis

Regarding the primary endpoint, the null hypothesis is that there is no difference in the mean change from baseline in CDR-SB at 24 months between elenbecestat (E2609) 50 mg per day and placebo; the corresponding alternative hypothesis is that there is a difference in the mean change from baseline in CDR-SB at 24 months between elenbecestat (E2609) 50 mg per day and placebo.

The primary analysis will be based on the intent to treat (ITT) philosophy without regard to adherence to treatment. The analysis will be performed by using a linear mixed effects model for repeated measures (MMRM) on the FAS. The MMRM model will include baseline CDR-SB as a

covariate, with treatment group, visit, randomization stratification variables (ie, region [7 levels], clinical dementia [yes, no], and concurrent AD medication use at randomization (Visit 2) [yes, no]), and treatment group-by-visit interaction as fixed effects. An unstructured covariance matrix will be employed to model the covariance of within subject effect; if MMRM fails to converge then a covariance structure with fewer parameters from the following list will be employed according to the prespecified order in the list until the MMRM converges. The list of covariance structure will include Heterogeneous Toeplitz, Toeplitz, Heterogeneous Compound Symmetry, and Compound Symmetry. This primary analysis will include all observed post baseline data of the change from baseline in CDR-SB without imputation of missing values. The least squares (LS) means and difference in LS means between elenbecestat (E2609) treatment group and placebo, and corresponding 95% CI will be presented.

Sensitivity Analyses

- 1). An MMRM analysis will be performed on the PPS.
- 2). To minimize the impact of change in concomitant AD medications, an MMRM analysis will be conducted on both FAS and PPS, by censoring the data after initiation of new AD medications (AChEI or memantine) and/or change in dose of current AD medications.
- 3). An analysis of covariance (ANCOVA) model will be used after multiple imputation to evaluate the impact of missing data in both FAS and PPS. The model will include baseline CDR-SB as a covariate, with treatment group and randomization stratification variables as factors.

Analysis for Chinese Subjects

LS mean and 95% CI for the difference between treatment groups as well as LS means and SE for each treatment group will be estimated using MMRM similar to the primary analysis. The treatment effect in Chinese subjects will be examined against the overall population using a forest plot.

5.4.2 Secondary Efficacy Analyses

The secondary endpoints are:

- Time to worsening of CDR scores by 24 months (eg, the worsening of global CDR score is defined as an increase from baseline by at least 0.5 points on the global CDR scale on 2 consecutive scheduled visits at which global CDR is undertaken)
- Time to conversion to dementia by 24 months for subjects who were not clinically staged as dementia at Baseline based on clinical diagnosis
- The rate of change over time (mean slope) based on CDR-SB score over 24 months
- Change from baseline in CDR-SB at 27 months (ie, 24 months of treatment plus 3 months posttreatment follow-up)

- Change from baseline in ADAS-cog₁₄, MMSE, and FAQ at 24 months
- Change from baseline in ADAS-cog₁₄ Word List (immediate recall and delayed recall) at 24 months

Time to worsening of CDR scores by 24 months

Time to worsening of CDR scores by 24 months will be analyzed on the FAS using a Cox regression model for treatment effect, adjusting for randomization stratification factors. Time to worsening of a CDR score is defined as time from randomization to worsening of the CDR score (ie, the first worsening - increase from baseline by at least 0.5 points on the global CDR score, in 2 consecutive scheduled visits). For subjects whose CDR scores have not worsened by the end of study, the time to worsening of the CDR score will be censored at the date of last CDR assessment for these subjects.

Time to conversion to dementia by 24 months for subjects who were not clinically staged as dementia at Baseline based on clinical diagnosis

This endpoint will be analyzed on the FAS using a Cox regression model for treatment effect, adjusting for randomization stratification factors. Proportion of subjects with dementia diagnosis at 24 months will be estimated using Kaplan-Meier method based on time to conversion to dementia in clinical diagnosis. Time to conversion to dementia for subjects who were not clinically staged as dementia at baseline is defined as time from randomization to conversion to dementia in clinical diagnosis. For subjects without clinical dementia by the end of study, the time to conversion to dementia will be censored at the date of last dementia diagnosis.

The diagnosis and clinical disease staging will be verified via a central review process and adjudicated if necessary (adjudication will only occur when there is a discrepancy between the diagnosis and clinical disease staging made by the site compared to that determined by the central review process; moreover, where adjudication is required, it will be undertaken by an independent assessor(s)).

The rate of change over time (mean slope) based on CDR-SB score over 24 months

The rate of change over time (mean slope) for the change from baseline in CDR-SB will be analyzed using linear mixed effects (LME) models for multivariate normal data derived from a random coefficient model (slope analysis), where the mean slope in each group depends on a continuous assessment time. The LME model will include baseline CDR-SB, randomization stratification variables, assessment time, and treatment group-by-assessment time.

Other continuous endpoints

The other continuous secondary efficacy endpoints will be analyzed using the same MMRM model as the primary efficacy analysis to compare elenbecostat (E2609) 50 mg versus placebo on the FAS, using baseline value corresponding to the response variable in the model. These endpoints include:

- Change from baseline in CDR-SB at 27 months (ie, 24 months of treatment plus 3 months posttreatment follow-up)
- Change from baseline in ADAS-cog₁₄, MMSE, and FAQ at 24 months
- Change from baseline in ADAS-cog₁₄ Word List (immediate recall and delayed recall) at 24 months

With regard to the change from baseline in ADAS-cog₁₄ Word List, it includes the immediate and delayed recall tasks, their scores will be part of the ADAS-cog₁₄ assessment (Item 1 and 4).

5.4.3 Biomarker Endpoints

The biomarker endpoints are changes from baseline in:

- Amyloid PET SUVR composite at 24 months for brain amyloid levels
- CSF biomarkers t-tau and p-tau at 24 months
- CSF amyloid biomarkers A β (1-40), A β (1-42), and A β (1-x) at 24 months
- Total hippocampal volume at 24 months using vMRI
- Preservation of connectivity on fMRI at 24 months

The analysis of the above endpoints will be performed by using MMRM or ANCOVA model, without adjustment for multiplicity or sequential testing. For each endpoint, the treatment effect for elenbecestat (E2609) 50 mg per day versus placebo will be tested at a significance level of 2-sided $\alpha = 0.05$.

The relationship between clinical changes (CDR-SB, ADAS-cog₁₄, MMSE, and FAQ) and changes in the biomarkers (amyloid PET, CSF t-tau and p-tau, vMRI, and fMRI) at 24 months, will be evaluated using an ANCOVA model. Changes in clinical scales at 24 months will be the response variables and either continuous or categorical change of biomarkers will be independent variables. The ANCOVA model will also include baseline value of clinical scale as a covariate, randomization stratification variables and treatment group as factors, and other terms as appropriate.

The relationship between exposure (in CSF, plasma) of elenbecestat (E2609) with potential biomarkers of Alzheimer's disease as deemed appropriate will be evaluated using ANCOVA model with changes in biomarker at 24 months as response variables and exposure variables (in CSF, plasma) of elenbecestat (E2609) as independent variables.

5.4.4 Exploratory Endpoints

The exploratory endpoints are:

- Time to change of concomitant AD treatment (ie, dose increase and/or initiation of treatment with AChEI or memantine after randomization) by 24 months
- The proportion of subjects at 24 months who received dose increases and/or initiation of treatment with AChEI or memantine after randomization
- The rate of change over time (mean slope) based on NPI-10 item score over 24 months
- Change from baseline in NPI-10 item at 24 months
- Change from baseline in EQ-5D (subject self-reported, study partner self-reported, and subject measured by proxy) and QOL-AD (subject and study partner) at 24 months
- Change from baseline in Zarit's Burden Interview at 24 months

Time to change of concomitant AD treatment will be analyzed similarly as that used for the time to conversion to dementia based on clinical diagnosis, as described in the 2nd endpoints. Time to change of concomitant AD treatment is defined as time from randomization to the first dose increase and/or initiation of treatment with AChEI or memantine after randomization. For subjects without any change of concomitant AD treatment by the end of study, the time to change of concomitant AD treatment will be censored at the date of last assessment of concomitant medication.

The proportion of subjects with any change of concomitant AD treatment at 24 months will be analyzed similarly as that used for the proportion of subjects with dementia diagnosis at 24 months, as described in section 6.4.2.

The rate of change over time (mean slope) based on change from baseline in the NPI-10 item will be analyzed in a manner similar as that used for the rate of change over time (mean slope) for the change from baseline in CDR-SB, as described in section 6.4.2.

Analysis of the change from baseline exploratory endpoints will be performed to compare elenbecestat (E2609) versus placebo by using MMRM or ANCOVA model. For each of them, the treatment effect of elenbecestat (E2609) 50 mg per day versus placebo will be tested at a significance level of 2-sided $\alpha = 0.05$. These endpoints include:

- Change from baseline in NPI-10 item at 24 months
- Change from baseline in EQ-5D (subject self-reported, study partner self-reported, and subject measured by proxy) and QOL-AD (subject and study partner) at 24 months
- Change from baseline in Zarit's Burden Interview at 24 months

5.5 SAFETY ANALYSES

Evaluations of safety will be performed on the Safety Analysis Set. The incidence of AEs, out-of-normal-range laboratory safety test variables, abnormal ECG findings, and out-of-range vital signs, suicidality, results of the sleep questionnaire, along with change from baseline in laboratory safety test variables, ECGs, and vital sign measurements will be summarized by treatment group.

5.5.1 Extent of Exposure

The Duration of exposure to study drug will be summarized as cumulative extent of exposure in categories with 3-month increment. The cumulative number and percent of subjects in each applicable exposure category will be presented by treatment group. Duration of exposure will be summarized using descriptive statistics as well as by 3-month duration categories using counts. The number and percent of subjects within each duration category will be presented by treatment group. Overall exposure (number of subject-months) is defined as summation over all subjects' exposure durations and will be summarized by treatment group.

5.5.2 Adverse Events

The AE verbatim descriptions (investigator terms from the eCRF) will be classified into standardized medical terminology using the Medical Dictionary for Regulatory Activities (MedDRA). AEs will be coded to the MedDRA (Version 19.0 or higher) lower level term closest to the verbatim term. The linked MedDRA PT and primary system organ class (SOC) are also captured in the database.

A TEAE is defined as:

- An AE that emerges during treatment within 4 weeks of the last dose of study drug, having been absent at pretreatment (Baseline) or
- Reemerges during treatment, having been present at pretreatment (Baseline) but stopped before treatment, or
- Worsens in severity during treatment relative to the pretreatment state, when the AE is continuous.

Only those AEs that are treatment-emergent will be included in summary tables. All AEs, treatment-emergent or otherwise, will be presented in subject data listings.

The TEAEs will be summarized by treatment group on the Safety Analysis Set. The incidence of TEAEs will be reported as the number (percentage) of subjects with TEAEs by SOC and PT. A subject will be counted only once within an SOC and PT, even if the subject experienced more than 1 TEAE within a specific SOC and PT. The number (percentage) of subjects with TEAEs will also be summarized by maximum severity (mild, moderate, or severe). The number

(percentage) of subjects with TEAEs will also be summarized by relationship to study drug (Yes [related] and No [not related]).

The number (percentage) of subjects with treatment-related TEAEs will be summarized by SOC and PT. Treatment-related TEAEs include those events considered by the investigator to be related to study drug. The number (percentage) of subjects with treatment-related TEAEs will also be summarized by maximum severity (mild, moderate, or severe).

AEs will be summarized by the following subgroups: region, concurrent treatment with AChEIs or memantine (no, yes), and clinical dementia (no, yes).

The number (percentage) of subjects with TEAEs leading to death will be summarized by MedDRA SOC and PT for each treatment group. A subject data listing of all AEs leading to death will be provided. The number (percentage) of subjects with treatment-emergent SAEs will be summarized by MedDRA SOC and PT for each treatment group. A subject data listing of all SAEs will be provided. The number (percentage) of subjects with TEAEs leading to discontinuation from study drug will be summarized by MedDRA SOC and PT for each treatment group. A subject data listing of all AEs leading to discontinuation from study drug will be provided.

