The maximum estimated duration for each subject in the Core Study is approximately 29 months (ie, 2 months Prerandomization Phase, followed by 24 months of blinded treatment period and a 3 month follow-up period in the Randomization Phase).

[figure not shown]
The Core Study will consist of Prerandomization and Randomization Phases. The Prerandomization Phase starts with consent and ends with randomization, and has a duration of up to 50 days (plus an additional window of up to 30 days if required). Subjects who participate in the optional longitudinal tau PET substudy will be permitted an additional window of up to 5 days (resulting in a total of up to 85 days) in order to accommodate the additional tau PET scan required to be performed during prerandomization. Screening assessments/procedures have been organized into 5 distinct tiers. All assessments and procedures in each tier should be completed, and eligibility to continue confirmed, before any assessments/procedures from the next tier commence. All Screening Visit assessments must be completed in the tiers as instructed, and eligibility to continue in the study confirmed, before any Visit 2 assessments commence. All subjects will be assessed for eligibility using cognitive assessments to confirm that subjects meet the diagnostic criteria for EAD including MCI due to AD and the early stages of mild AD, and that they do not have other medical conditions that may interfere with study participation. The diagnosis and clinical disease staging will be verified via a central review process and adjudicated if necessary (adjudication will only occur when there is a discrepancy between the diagnosis and clinical disease staging made by the site compared to that determined by the central review process; moreover, where adjudication is required, it will be undertaken by an independent assessor(s)).

The Randomization Phase consists of a Treatment Period and a Follow-Up Period. The Treatment Period will last 24 months. Subjects will be randomized at Visit 2 (Day 1) to receive elenbecestat 50 mg per day or placebo administered orally, once daily (QD) in the morning with or without food. The Follow-up Period will last for 12 weeks and is required for all subjects, regardless of whether they completed all 24 months of treatment or discontinued study drug early.

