5.2.2 Subject Disposition

The number of subjects screened, the number (percent) of subjects who failed screening, and the reasons for screen failure will be summarized, based on data reported on the Screening Disposition electronic case report form (eCRF). The primary reasons for screen failures (did not meet inclusion or met exclusion criteria, adverse event (AE), lost to follow-up, withdrawal of consent, and other) will be presented. The distribution of the number of randomized subjects enrolled by each site, country, and region will be summarized for each randomized treatment group and combined total.

Study Completion: the number (percent) of randomized and treated subjects who completed the study and who withdrew from the study will be summarized according to the primary reason for withdrawal and secondary reason(s) for withdrawal, based on data reported on the Subject Disposition (Study Phase) case report form (CRF). The number (percent) will be presented by treatment group and total subjects; randomized, not treated, treated, who completed the study, and withdrew from the study. The primary reasons for early withdrawal from the study are: AE, lost to follow-up, subject choice, inadequate therapeutic effect, withdrawal of consent, pregnancy, study terminated by sponsor, and other. The secondary reasons for early withdrawal from the study are: AE, subject choice, inadequate therapeutic effect, and other. This table will be summarized on the All Randomized Subjects, the Safety Analysis Set, and the FAS.

Completion of Study Treatment: the number (percent) of randomized and treated subjects who completed study drug and who discontinued early from study drug will be summarized according to the primary reason for early discontinuation (ED) and also according to secondary reason(s) for discontinuation, based on data reported on both the Subject Disposition (Study Phase) eCRF and ED from Study Drug eCRF. The number (percent) will be presented by treatment group and total subjects; randomized, not treated, treated, who completed study drug, and discontinued from study drug. The primary reasons for early discontinuation from the study drug are: AE,

subject choice, inadequate therapeutic effect, pregnancy, and other. The secondary reasons for early discontinuation from the study drug are: AE, subject choice, inadequate therapeutic effect, and other. This table will be summarized on the All Randomized Subjects, the Safety Analysis Set, and the FAS.

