5.5.2 Adverse Events

The AE verbatim descriptions (investigator terms from the eCRF) will be classified into standardized medical terminology using the MedDRA. AEs will be coded to the MedDRA (Version 22.0 or higher) lower level term closest to the verbatim term. The linked MedDRA PT and primary SOC are also captured in the database.

A treatment-emergent adverse event (TEAE) is defined as:

- An AE that emerges during treatment or within 4 weeks (28 days) following the last dose of study drug, having been absent at pretreatment (Baseline) or

- Reemerges during treatment or within 4 weeks (28 days) following the last dose of study drug, having been present at pretreatment (Baseline) but stopped before treatment, or
- Worsens in severity during treatment or within 4 weeks (28 days) following the last dose of study drug relative to the pretreatment state, when the AE is continuous.

Only those AEs that are treatment-emergent will be included in summary tables. All AEs, treatment-emergent or otherwise, will be presented in subject data listings.

The TEAEs will be summarized by treatment group on the Safety Analysis Set. The incidence of TEAEs will be reported as the number (percentage) of subjects with TEAEs by SOC and PT. A subject will be counted only once within an SOC and PT, even if the subject experienced more than 1 TEAE within a specific SOC and PT. The number (percentage) of subjects with TEAEs will also be summarized by maximum severity (mild, moderate, or severe). The number (percentage) of subjects with TEAEs will also be summarized by relationship to study drug (Yes [related] and No [not related]).

The number (percentage) of subjects with treatment-related TEAEs will be summarized by SOC and PT. Treatment-related TEAEs include those events considered by the investigator to be related to study drug. The number (percentage) of subjects with treatment-related TEAEs will also be summarized by maximum severity (mild, moderate, or severe).

AEs will be summarized by the following subgroups: region, concurrent AD medication use (yes, no), and clinical disease staging (MCI due to AD, early stage of mild AD).

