The number (percentage) of subjects with TEAEs leading to death will be summarized by MedDRA SOC and PT for each treatment group. A subject data listing of all AEs leading to death will be provided. The number (percentage) of subjects with treatment-emergent serious adverse events (SAEs) will be summarized by MedDRA SOC and PT for each treatment group. A subject data listing of all SAEs will be provided. The number (percentage) of subjects with treatment-emergent non-serious AEs will be summarized by MedDRA SOC and PT for each treatment group. The number (percentage) of subjects with TEAEs leading to discontinuation from study drug will be summarized by MedDRA SOC and PT for each treatment group. A subject data listing of all AEs leading to discontinuation from study drug will be provided. The number (percentage) of subjects with TEAEs leading to interruption of study drug will be summarized by MedDRA SOC and PT for each treatment group. A subject data listing of all AEs leading to interruption of study drug will be provided. The number (percentage) of subjects with TEAEs leading to concomitant treatment administration will be summarized by MedDRA SOC and PT for each treatment group. A subject data listing of all AEs leading to concomitant treatment administration will be provided.

The number (percentage) of subjects with TEAEs of special interest will be summarized by MedDRA SOC and PT for each treatment group. TEAEs relating to abnormal dreams, nightmares, or sleep terror will be defined as TEAEs classified by the category recorded in Adverse event CRF or completing sleep/abnormal dream questionnaire. The number

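### Fatal and serious adverse events that start more than 28 days after the last dose are listed but enter no by-arm table, although follow-up runs for 84 days

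*SAP*

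**What the plan says.** The governing text is SAP v2.0, which covers both studies. In section 5.5.2 the first arm of the treatment-emergent definition is "An AE that emerges during treatment or within 4 weeks (28 days) following the last dose of study drug", provided the event was absent at baseline. The arms for recurring and for worsening events carry the same 28-day limit. A general rule follows: "Only those AEs that are treatment-emergent will be included in summary tables". Everything else goes to listings: "All AEs, treatment-emergent or otherwise, will be presented in subject data listings".

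The rule is then applied to the gravest outcomes. For deaths: "The number (percentage) of subjects with TEAEs leading to death will be summarized by MedDRA SOC and PT for each treatment group". For serious events: "The number (percentage) of subjects with treatment-emergent serious adverse events (SAEs) will be summarized by MedDRA SOC and PT for each treatment group". Each table is paired with a subject listing of all such events, whether or not they are treatment-emergent.

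Section 3.2 sets the observation period after drug: "The Follow-up Period will last for 12 weeks and is required for all subjects", including those who stop early. Section 5.2.2 gives the primary reasons for leaving the study, tabulated by arm: "AE, lost to follow-up, subject choice, inadequate therapeutic effect, withdrawal of consent, pregnancy, study terminated by sponsor, and other".

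SAP v1.0 for each study has the same structure, with a less clearly worded window ("An AE that emerges during treatment within 4 weeks of the last dose of study drug") and with recurring or worsening events counted only during treatment. Those plans are superseded, so the point rests on v2.0.

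**The concern.** All-cause death and SAEs are the safety outcomes for which a reader most expects a complete count by arm. Here both tables stop at 28 days after the last dose, while required follow-up continues to 84 days. A fatal or serious event that starts on day 29 or later does not appear in any by-arm table.

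The plan does not treat this period as uninformative elsewhere. Section 5.5.3 summarises laboratory values by arm at the 12-week follow-up visit. Section 5.5.5 does so for ECG interpretation, and section 5.5.6 for white matter disease on MRI. So a laboratory value taken 12 weeks after the last dose is tabulated by arm, while an SAE starting 8 weeks after it is not.

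What is at stake is the completeness of the risk comparison in the final report. The DSMB's form of 11 September 2019 recommended stopping on an unfavourable risk-benefit balance, so that comparison will be read closely.

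**Working it through.** The plan states no figure for this point, so there is nothing to reproduce. The check is window arithmetic plus a search for any other by-arm count.

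**Inputs**
- Table window after last dose: 28 days (v2.0 section 5.5.2).
- Required follow-up: 12 weeks = 84 days (v2.0 section 3.2).
- Full treatment period: 729 days (v2.0 section 5.2.6, overall compliance).

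**Step 1. Share of required follow-up outside the tables**
- (84 − 28) / 84 = 56 / 84 = 66.7%.

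**Step 2. The same 56 days against a completer's whole time on study**
- Time on study: 729 + 84 = 813 days.
- Untabulated share: 56 / 813 = 6.9%.

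**Step 3. Scale**
- Per subject with full follow-up: 56 / 365.25 = 0.153 person-years.
- For 1,000 such subjects (an illustrative number; the SAP does not give one): 1,000 × 0.153 = 153 person-years. For 1,500: 1,500 × 56 / 365.25 = 230 person-years.
- Converting this into deaths or SAEs would need event rates. The SAP gives none, so I stop here.

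**Step 4. Is there another by-arm count?**

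| Output in v2.0 | By arm? | Covers onset on days 29 to 84? |
|---|---|---|
| TEAEs leading to death (5.5.2) | Yes | No |
| Treatment-emergent SAEs (5.5.2) | Yes | No |
| Listings of all AEs, all fatal AEs, all SAEs (5.5.2) | No, subject level | Yes |
| Study withdrawal by reason (5.2.2) | Yes | Partly: a late fatal event may fall under AE or other, but death is not a category |

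No row gives a by-arm count of all deaths or of all SAEs, and no other section plans one.

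**Step 5. What the cut-off acts on**

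The limit applies to the start, recurrence or worsening of the event, not to the date of death. A subject who dies on day 60 from an event that began on day 20 is in the death table. A subject who dies on day 60 from an event that began on day 40 is not.

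**The case against.** The case against is that the SAP is consistent on this point. It states one window, applies it throughout, and lists everything outside it. No event is lost: the listings of all fatal AEs and all SAEs contain the late ones, and deaths may be few enough to count by hand. For a completer the untabulated time is 6.9% of time on study. On this view, more tables are a matter of preference.

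Much of that stands. The events are recoverable, and this is neither a contradiction nor a misstated figure. What remains is that a hand count from listings is not a planned comparison, and that the rule is an explicit choice in the SAP rather than detail left to the protocol.

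Three stronger readings are tempting, and the documents do not support them.

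- A reader might infer that every death after day 28 is left out. The onset rule in Step 5 shows otherwise.
- A reader might infer that all later follow-up of subjects who stopped drug is also excluded, and that the arm with more early stops therefore loses more events. Section 3.2 asks these subjects back at 12 and 24 months for a clinical assessment, and section 8.2 names those visits only in its efficacy rule. The SAP does not say that AEs are collected there. It gives no stop rates by arm, and early termination shortened this time in any case. A difference between arms cannot be shown.
- A reader might link the gap to the DSMB's decision. Nothing indicates that the board's conclusion turned on events after day 28, and under its charter it also received SAE line listings and individual reports.

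**Conclusion.** The point holds for the 12-week follow-up. Under v2.0 section 5.5.2, fatal AEs and SAEs that start in the last 56 of 84 follow-up days (67%) appear only in listings. No by-arm count of all deaths or all SAEs is planned.

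This rests on the wording of v2.0 sections 3.2, 5.2.2 and 5.5.2 and on no assumed rate. The number of events affected is unknown and may be small. Any effect beyond the 12 weeks depends on the AE collection period, which the SAP does not give. I rate it a cheap improvement, not an error that undermines the safety analysis.

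**What to change.** In v2.0 section 5.5.2, qualify the sentence "Only those AEs that are treatment-emergent will be included in summary tables" so that it does not apply to deaths or SAEs. Then add two tables by treatment group, placed beside the existing treatment-emergent ones:

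1. all deaths from any cause;
2. all SAEs by SOC and PT.

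Both should cover everything recorded from first dose to the end of Core Study participation, and both should show person-time over that period. Ending at the Core Study keeps open-label Extension events out of the randomised comparison.

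The cost is one amended sentence and two tables, built from events the SAP already plans to list. No new data are needed. The downside is that the added tables also show off-drug events, which is why the treatment-emergent tables should stay next to them.
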